9.2.2 Analysis of Efficacy

9.2.2.1 Primary efficacy analysis

The primary efficacy analysis is to evaluate the change in trough-cuff seated SBP from baseline to Day 84 for the KBP-5074 doses compared to placebo. The endpoint for each patient is defined as the Day 84 cuff seated SBP measurement. If the measurement at this visit is missing or the patient discontinues early, the last post-baseline measurement during the double-blind period will be used.

The primary efficacy analysis will be carried out using a 2-way analysis of covariance (ANCOVA) model with treatment, baseline eGFR level (≥ 30 versus < 30 mL/min/1.73 m²), and background antihypertensive medication (2 or more) as factors, and the baseline SBP value as a covariate. The least-squares means, standard errors, and the 2-tailed 95% confidence intervals (CIs) for each treatment group and for the comparison will be estimated. The treatment difference between KBP-5074 doses and placebo will be estimated from the ANCOVA model. No multiple comparison adjustment will be used for this Phase 2 study.

The primary efficacy analysis will be based on the ITT Population. Other imputation methods for the primary efficacy endpoint will be explored. The supportive analysis will be carried out for the primary efficacy variable based on the Per-Protocol Population to examine the impact due to premature dropouts and/or major protocol deviations or violations.

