4.3 Withdrawal Criteria

Participation of a patient in this clinical study may be discontinued for any of the following reasons:

- The patient withdraws consent or requests discontinuation from the study for any reason;
- Significant protocol violation, including major protocol violations, such as taking prohibited medication or inability to comply with protocol procedure;

- Any clinically significant adverse event, severe laboratory abnormality, intercurrent illness, or other medical condition that indicates to the Investigator that continued participation is not in the best interest of the patient, including:
 - Hypertensive Emergency;
 - Hyperkalemia defined in Table 1; or
 - Sustained increase in serum creatinine defined as an increase > 50% in serum creatinine from baseline and confirmed by a repeated test (see Section 8.13);
- Pregnancy;
- Termination of the study by the Sponsor or regulatory authority; or
- Lost to follow-up.

If a patient withdraws prematurely from the study due to the above criteria or any other reason, study staff should make every effort to complete the full panel of assessments scheduled for the Early Termination Visit (see Section 6.6). The reason for patient withdrawal must be documented in the electronic Case Report Form (eCRF).

In the case of patients lost to follow-up, attempts to contact the patient must be made and documented in the patient's medical records.

Withdrawn patients will not be replaced.

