5 STUDY TREATMENTS

5.1 Treatment Groups

After completion of the screening period and qualifying Screening Visit, patients who meet all eligibility criteria (except those criteria scheduled to be assessed after the Screening Visit) will enter a 2-week run-in period. During this time, all patients will be given open-label placebo.

At the Day 1 Visit (scheduled within 4 ± 2 days after the end of the run-in period [Visit 3]), eligible patients will be randomized by Interactive Response Technology (IRT) in a 1:1:1 ratio to the following treatment groups:

- KBP-5074 0.25 mg QD orally,
- KBP-5074 0.5 mg QD orally, or
- Placebo QD orally

The duration of the double-blind treatment period will be 84 days. Patients will remain on their stable antihypertensive medication (ie, no change in antihypertensive medication) throughout the entire study (including both the run-in and treatment periods). The dose of diuretic may be adjusted based on developing or resolved edema, weight gain or loss, or pulmonary congestion.

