5.4 Breaking the Blind

At all times, study personnel will attempt to safeguard the integrity of the blinding in order to minimize bias in the conduct of the study. Breaking of the blind should not occur except in the case of a medical emergency and should occur after discussion with the Medical Monitor. In such a case, the Investigator may access this information by contacting the Sponsor or its designee. If the blind is broken for an individual patient, the blinding should be preserved for the remainder of the patients throughout the duration of the study. In such a case, study personnel may be notified of that individual patient's treatment assignment without jeopardizing study blinding for the overall study.

If the blind is broken for a patient, the patient may or may not be asked to withdraw from the study. This decision will be based on Investigator consultation with the Medical Monitor. All patients will be asked to continue study visits to the end of the study whether or not they remain on study drug. If a patient must temporarily discontinue study drug, they may or may not be able to restart study drug. This decision will be based on Investigator consultation with the Medical Monitor.

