9 STATISTICS

9.1 Analysis Populations

The Intent-to-Treat (ITT) Population will consist of all randomized patients who take at least 1 dose of randomized study drug, have a baseline SBP measurement, and have at least 1 post-randomization SBP measurement. The ITT Population is the primary analysis population. All efficacy analyses will be performed for the ITT Population.

The Per-Protocol Population will include all ITT patients who have completed the 84-day double-blind treatment period without any major protocol deviations or violations. The Per-Protocol Population will be used to assess robustness of the primary analysis results. The major protocol deviations will be pre-specified prior to unblinding treatment codes for analyses.

The Safety Population will include all randomized patients who receive at least 1 dose of randomized study drug.

The PPK Population will include all randomized patients who receive at least 1 dose of randomized study drug and have at least 1 measurable concentration of total KBP-5074.

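### The only named check on early dropout is the Per-Protocol analysis, which contains no early leaver and so cannot test the carried-forward SBP values

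*Combined protocol and SAP*

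**What the plan says.** **Primary rule.** Section 9.2.2.1 takes the Day 84 cuff SBP. Where it is missing, or where "the patient discontinues early, the last post-baseline measurement during the double-blind period will be used", an earlier reading stands in.

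**Checks on that rule.** The same section has a supportive analysis "based on the Per-Protocol Population to examine the impact due to premature dropouts and/or major protocol deviations or violations". It adds: "Other imputation methods for the primary efficacy endpoint will be explored". It gives no method, assumption or population for these.

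**Who is in Per-Protocol.** Section 9.1 admits ITT patients "who have completed the 84-day double-blind treatment period without any major protocol deviations or violations".

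**Follow-up after stopping drug.**
- Section 4.3 says: "Participation of a patient in this clinical study may be discontinued for any of the following reasons". The medical reasons apply where the condition "indicates to the Investigator that continued participation is not in the best interest of the patient", and they include hypertensive emergency, Table 1 hyperkalaemia and a sustained creatinine rise. An Early Termination Visit follows.
- Sections 8.12 to 8.14 treat the same events as reasons to stop study drug. In Table 1, only the column for potassium of 6.0 mmol/L or more adds that visits continue.
- Section 5.4 says: "All patients will be asked to continue study visits to the end of the study whether or not they remain on study drug".

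**The concern.** The check assigned to dropout is run in a population from which early leavers have been removed. It can show what happens when their carried-forward values are left out. It cannot show whether those values resemble what the patients' SBP would have been at Day 84.

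This matters if an active-arm patient stops drug, an on-drug reading is carried forward, and the effect has faded by Day 84. Carry-forward credits that patient with the full effect, and Per-Protocol drops the patient. In some settings both give the same figure, and a reader would take the agreement as robustness. A missing-at-random model fitted to on-drug data alone can give that figure too, so an alternative chosen later need not expose the problem.

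Stops on active drug are plausible: Section 5.2 reports a possible link between exposure and hyperkalaemia, and higher exposure in severe CKD. The documents give no rate by arm. Off-drug Day 84 readings that are not collected during the trial cannot be recovered later.

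**Working it through.** **Inputs.** From 9.2.7: difference 5 mmHg, SD of change 15 mmHg, 80 per group, dropout 10% to 15%. From 9.2.2.1: two-sided 95% CI. Assumed, because the documents are silent: the share of active patients who stop with an on-drug value carried forward (2.5% to 15%, the top being the planned all-cause dropout) and the part of the effect lost by Day 84 (half to all).

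**The plan's own figure.** n = 2 × (1.96 × 15 / 5)² = 69.15, so 70 evaluable per group. Inflated: 70/0.875 = 80, and 70/0.87 = 80.5, so 81. This reproduces the stated 80 and the Table 2 entry of 81. The sample size is not in question.

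**Patients affected.** 10% to 15% of 80 is 8 to 12 per arm, or 24 to 36 of 240. All are outside Per-Protocol.

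**Size of the overstatement** = share stopped × effect lost:
- 0.025 × 2.5 = 0.06 mmHg
- 0.10 × 5 = 0.50 mmHg
- 0.15 × 2.5 = 0.375 mmHg
- 0.15 × 5 = 0.75 mmHg

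SE = 15 × √(2/80) = 2.37, so the maximum is 0.75/2.37 = 0.32 SE. The CI half-width is 1.96 × 2.37 = 4.65, which leaves 5 − 4.65 = 0.35 mmHg of margin at an observed 5 mmHg. The overstatement is near zero if the carried value is an Early Termination reading taken after the effect has gone.

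**Simulation.** 3000 runs, 80 per arm, visits Day 7 to Day 84, SD 15 per visit with correlation 0.5 (SD of change 15), effect -5 at every on-drug visit, stops after Day 14 to 56 unrelated to SBP, no rescue, ANCOVA on baseline SBP only, Monte Carlo SE about 0.04. Estimates in mmHg:

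| Stops active / placebo; effect after stop | Carry-forward | Per-Protocol | Missing-at-random, on-drug data | All collected Day 84 | Placebo-based |
|---|---|---|---|---|---|
| 10% / 10%; lost | -5.03 | -5.03 | -5.03 | -4.52 | -4.53 |
| 10% / 0%; lost | -5.02 | -5.02 | -5.02 | -4.52 | -4.51 |
| 15% / 15%; lost | -4.97 | -4.99 | -4.98 | -4.23 | -4.24 |
| 10% / 10%; half persists | -4.96 | -4.97 | -4.96 | -4.70 | -4.47 |
| 15% / 15%; half persists | -4.95 | -4.96 | -4.95 | -4.58 | -4.21 |

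The first three columns agree in every row and miss the fourth. The placebo stop rate does not drive the gap.

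**Where the agreement fails.** It depends on a constant effect and on stops unrelated to SBP. With an effect that builds to Day 84 and 15% random stops, carry-forward gives -4.78 and Per-Protocol -5.02. With stops driven by high SBP (about 7% active, 11% placebo), they give -5.25 and -4.85. Other runs of these two kinds gave -4.51 against -4.92, and -5.91 against -4.58. A gap of that sort would alert the reader, but would not show which figure is nearer the Day 84 truth.

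**The case against.** - **Comparing results with and without dropouts does show their influence, and that is all 9.2.2.1 claims.** This stands in part. Per-Protocol is informative about influence, and it can separate from carry-forward. It still says nothing about whether the carried values are right.
- **The plan promises other imputation methods.** It does, and this is credited. With no method named, nothing ensures that the one chosen will use off-drug data or a less favourable assumption.
- **The word overstate presupposes an effect regardless of stopping drug.** This stands. The plan states no estimand, and an on-drug effect is a legitimate Phase 2 question. The figures apply only to the first question.
- **The size is small and rests on extreme inputs.** This stands. The 0.75 mmHg figure needs all of a 15% dropout to carry an on-drug value, lose the whole effect and receive no rescue. The 2.5% floor has no source in the documents.
- **Placebo-based imputation has its own error.** This stands. With half the effect persisting and 15% stops, it errs by 4.58 − 4.21 = 0.37 mmHg. Carry-forward errs by the same amount in the other direction (4.95 − 4.58). The mixed analysis proposed below was not simulated. Its imputation error should shrink as more off-drug Day 84 readings are collected.

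A reader might also infer that 4.3 contradicts 5.4. The documents do not support that: 4.3 is permissive, while 5.4 addresses all patients, although it sits under the heading on breaking the blind. Nor do they show that early discontinuation replaces a Day 84 SBP that was in fact collected. Appendix A footnote 2 reserves the Early Termination Visit for patients who leave the study, and Section 5.1 says: "The duration of the double-blind treatment period will be 84 days". Both are points to clarify.

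**Conclusion.** The concern holds in this form. By the definitions in 9.1 and 9.2.2.1, the one named dropout check contains no early leaver, and no other named analysis tests the carried-forward values. This needs no clinical assumption.

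The consequence is conditional. Where stops are unrelated to SBP and the effect is constant from early visits, agreement near -5.0 can hide an all-collected Day 84 value near -4.5 (10% stops, full loss). Across the assumed range the overstatement is 0.06 to 0.75 mmHg, at most 0.32 SE, for an effect regardless of stopping drug.

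A stronger reading would be that the primary result is biased, or that the two analyses must agree. The documents support neither: they give no stop rate by arm and no rate of loss of effect, and the two analyses can diverge. The change is worth making because it is cheap and because uncollected readings are lost for good.

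**What to change.** 1. **Section 9.2.2.1.** Keep the current primary analysis. Add one pre-specified sensitivity analysis in all ITT patients that uses all collected SBP, including off-drug values, with placebo-based imputation where Day 84 is still missing. List rescue antihypertensives and diuretic changes beside it. Describe Per-Protocol as a check on protocol deviations, not on dropout.
2. **Sections 4.3 and 6.6.** Cross-refer to 5.4: hypertensive emergency, Table 1 hyperkalaemia and creatinine rise stop study drug, and visits continue to Day 84 unless consent is withdrawn.
3. **Clarify in 9.2.2.1** that early discontinuation means leaving the study, and whether an Early Termination reading may be carried forward.

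**Cost.** Some wording, one extra analysis, and visits that 5.4 already requests. Placebo-based imputation is conservative if some effect persists: about 0.2 mmHg at 10% stops (4.70 − 4.47) and 0.4 at 15%, if every stopper's Day 84 value is imputed and half the effect remains. Off-drug readings may reflect rescue treatment or a higher diuretic dose, hence the listing.

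Replacing the primary analysis would cost more. The chance that the CI excludes 0, Φ(d/2.37 − 1.96), falls from 56% at a true 5 mmHg to 48% at 4.5 and 43% at 4.25, and an observed 4.5 would need 2 × (1.96 × 15 / 4.5)² = 85.4, so 86 evaluable per group. Adding the analysis beside the current primary avoids this.

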9.2.2.2 Secondary efficacy analyses

For continuous secondary efficacy variables, the same ANCOVA model will be used as the primary efficacy analysis. For categorical data, logistic regression or chi-square test will be used. Treatment effects will be evaluated between KBP-5074 doses and placebo.

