3 STUDY DESCRIPTION

3.1 Summary of Study Design

This is a Phase 2, randomized, double-blind, placebo-controlled, multi-center study to assess the efficacy, safety, and PK of KBP-5074 in patients with moderate-to-severe CKD and uncontrolled hypertension (Grade 1 to 2 systolic hypertension – ESC/ESH).

The study will enroll approximately 240 patients, randomized in a 1:1:1 ratio to 1 of 3 treatment groups (80 patients in each group): KBP-5074 0.25 mg QD, KBP-5074 0.5 mg QD, or placebo QD. Randomization will be stratified to balance enrollment for key variables that may influence safety and/or efficacy evaluations, including eGFR (\geq 30 versus < 30 mL/min/1.73 m²) and SBP (\geq 160 versus < 160 mmHg). Approximately 30% of patients enrolled in the study should have eGFR in the range of 15 to 29 mL/min/1.73 m². The study will be approximately 5 months in duration with 84 days of double-blind treatment.

The study will consist of up to a 4-week screening period, 2-week open-label (placebo) run-in period, 84-day double-blind treatment period, and a 4-week post-treatment safety follow-up period.

Plasma samples for PK analysis will be collected from all patients. A total of 4 PK samples will be collected from each patient, including at Day 1 (prior to discharge), Day 14 pre-dose, Day 28 pre-dose, and the End of Study Visit (Day 112)/Early Termination Visit. The pre-dose samples assume that patients will be dosed in the unit on the days above. If patients are not dosed in the unit on those days, a PK sample will be collected during each of these visits and the date and time of the last dose will be recorded.

Safety will be assessed systematically, and an independent data monitoring committee (IDMC) will perform cumulative reviews of safety data at regular intervals during the study.

Serum potassium levels, serum creatinine, and blood pressure will be closely monitored throughout the study and clinically significant changes will be reported as adverse events of special interest.

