6.4.10 Day 84 (Visit 10) ± 3 Days

The following procedures will be performed at Visit 10:

- Perform physical examination;
- Record weight;
- Calculate body mass index;
- Obtain vital signs including pulse rate, respiratory rate, and oral temperature;
- Obtain blood pressure;
 - O Blood pressures are to be obtained according to the AHA recommendations for accurate blood pressure measurement. Patients should avoid smoking, caffeine, or exercise within 30 minutes before measurement; empty his or her bladder; then sit quietly in a comfortable chair with back support for at least 10 minutes before measurement and remain still during the measurement. The patient's limb should be supported to measure blood pressure to ensure that the blood pressure cuff is at heart level, using the correct cuff size. Do not take the measurement over clothes. Blood pressure measurements should be performed in the

same arm throughout the study. Triplicate blood pressure measurements should be taken approximately 2 minutes apart with a validated, oscillometric upper arm blood pressure monitor. Trough cuff SBP and DBP values will be assessed based on the pre-defined blood pressure measurement guideline throughout the study. Pulse will be obtained simultaneously with blood pressure measurements;

- Obtain blood sample for clinical laboratory tests (central laboratory; see Appendix B);
- Obtain urine sample for:
 - o Urinalysis (central laboratory; see Appendix B);
 - o UACR; and
 - o 24-hour urine for UACR;
- Obtain serum sample for aldosterone;
- Obtain plasma sample for renin;
- Obtain serum sample for potassium (local and central laboratories);
- Obtain serum sample for creatinine (central laboratory);
- Obtain serum/plasma samples that will be stored at the central laboratory for determination of various additional biomarkers, including but not limited to galectin-3, NT-proBNP, IL-6, collagen biomarkers and CRP. The panel of biomarkers and time points for analysis will be determined prior to the database lock;
- Record adverse events and concomitant medications;
- Check study drug accountability and collect unused study drug; and
- Download 24-hour ABPM readings at site (for a subset of up to 40 patients per treatment group who agree to participate in 24-hour ABPM and still meet eligibility criteria at the end of the run-in period [Visit 3] who undergo 24-hour ABPM).

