7.2 Secondary Efficacy Assessments

Twenty-four-hour ABPM monitoring will be assessed at the visits indicated on the Schedule of Procedures (Appendix A) in a subset of up to 40 patients per treatment group. At the end of the run-in period (Visit 3), ABPM will only be assessed for those patients who agree to participate in 24-hour ABPM and still meet all of the eligibility criteria. Blood pressure and HR measurements will be obtained every 20 minutes during the interval of 06:00:00 hours to 21:59:59 hours (to coincide with the daytime, awake period) and every 30 minutes during the interval of 22:00:00 hours to 05:59:59 hours (to coincide with the nighttime, sleeping period).

During the 24-hour ABPM recording period, a diary will be provided to the patient. Instructions and training will be provided to the site staff, who will in turn provide instructions to the patient.

The key secondary efficacy variables include the following:

• Change in trough-cuff seated DBP from baseline to Day 84;

Note: Blood pressure must be measured in triplicate prior to study drug administration at the visits indicated on the Schedule of Procedures (Appendix A). Trough-cuff DBP values will be assessed based on the pre-defined blood pressure measure guideline throughout the study.

- Change in 24-hour mean, daytime mean, nighttime mean, morning mean, last 6 hours of the dosing interval mean, SBP, DBP, MAP, and HR from baseline to Day 84 as measured by 24-hour ABPM in a subset of up to 40 patients per treatment group; and
- Change and percent change in UACR from baseline to Day 84 (for patients with albuminuria [defined as UACR >300 mg/g] or microalbuminuria [defined as UACR in the range of 30 mg/g to 300 mg/g]).

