9.2 Statistical Methods

9.2.1 Demographic and Baseline Comparability

Patient disposition and analysis population data will be tabulated by treatment group with number and percentage of patients. Summary statistics will be provided by treatment group for demographics (eg, age, sex, race, and ethnicity) and for baseline efficacy variables (such as SBP, serum potassium, eGFR, creatinine, DBP, and UACR). For efficacy variables, baseline will be defined as the Day 1 (Visit 4) measurement. If the measurement at this visit is missing, then the last measurement prior to the first dose of randomized study drug will be used.

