APPENDIX A: SCHEDULE OF PROCEDURES

Study Period	Screening ¹ (≤ 4 weeks)	Placebo	-Label Run-In veeks)		Double-Blind Treatment							EOS	ET ²		
Study Day	≤ -42 days	≤ -18	≤ -4	-1	1	7	14	28	40	42	56	82	84	112	
Visit Visit	1	2	3	ABPM ^{3,4}	45	5	6	7	ABPM ⁴	8	9	ABPM ⁴	10	112	+
Visit Window	1			ADIM		±2 day			ADIM		days	ADIM	10	±5 days	\vdash
Assessment					-	LZ uay	 			 	l			±3 days	1
Signed informed consent	X														+
Eligibility assessment	X		X		X										+
Randomization	A		Λ		X										+
Demographics	X				Λ										-
Medical history	X					1	1		1					1	
Physical examination	X				X ⁶		ł	ł					X	X	X
Height (cm)	X				A								Λ	Λ	Λ
	X	X	X		v	v	X	X		X	X		v	X	X
Weight (kg)		Α	Λ		X	X	Α	Α		Α	A		X	Λ	A
Body mass index	X	₹7			3 7	1	1	W 7			37		X		37
Contact IRT	X	X			X	3 7	 	X			X			V	X
Triplicate standard 12-lead ECG ⁷	X	**	***		X	X	***	***		***	***		77	X	X
Vital signs (PR, RR, OT) ⁸	X X ¹⁰	X	X x 10		X X ¹¹	X	X X ¹¹	X X ¹¹		X	X		X	X	X
Blood pressure ^{8,9}	XIII	X	X ¹⁰		XII	X ¹¹	XII	XII		X ¹¹	X ¹¹		X	X	X
24-hour ABPM device placement				-					***			***			
and start ^{4,12}				X		ļ			X			X			12
24-hour ABPM download at site ⁴					X	 	 			X			X		X ¹³
HIV, HbsAg, and HCV	X														
Urine drug screen	X		X												
Clinical laboratory samples			15											l	
(central laboratory) ¹⁴	X		X ¹⁵		X	X	X	X		X	X		X	X	X
Serum potassium (local and															
central laboratories) ¹⁶	X		X		X	X	X	X		X	X		X	X	X
Serum creatinine (central														l	
laboratory)	X		X		X	X	X	X		X	X		X	X	X
Pregnancy test on WOCBP only ¹⁷	X				X									X	X
FSH ¹⁸	X														
Serum samples for aldosterone					X								X		X
Plasma samples for renin					X								X		X
Serum and plasma samples for															
additional biomarkers ¹⁹					X								X		X
Plasma samples for PK					X^{20}		X^{21}	X^{21}						X	X
Urine samples for UACR	X				X	X	X	X		X	X		X	X	X

Study Period	Screening ¹ (≤ 4 weeks)	Placeb	n-label o Run-In					Do	ukla Dlind	Tucatm	ont.			EOS	ET ²
		(2 weeks)			Double-Blind Treatment							E1-			
Study Day	≤ -42 days	≤-18	≤ -4	-1	1	7	14	28	40	42	56	82	84	112	
Visit	1	2	3	ABPM ^{3,4}	45	5	6	7	ABPM ⁴	8	9	ABPM ⁴	10	11	
Visit Window					±2 days			±3 days						±5 days	
Provide 24-hour urine collection instruction and supplies			X					X			X				
24-hour urine samples for UACR					X					X			X		
Adverse event and concomitant medications	X	X	X		X	X	X	X		X	X		X	X	X
Study drug instruction and dispensing		X ²²			X	X	X	X		X	X				

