APPENDIX B: CLINICAL LABORATORY ANALYTES

Standard Safety Chemistry Panel

Alanine aminotransferase
Albumin
Alkaline phosphatase
Aspartate aminotransferase
Blood urea nitrogen
Chloride
Albumin
Amylase
Bicarbonate
Calcium
Creatine kinase

Chloride Creatine Kinase

Creatinine Estimated glomerular filtration rate¹

Gamma-glutamyl transferase Glucose

Inorganic phosphorus Lactate dehydrogenase

Lipase Potassium
Sodium Total bilirubin
Total protein Uric acid

Calculated by the central laboratory using the Modification of Diet in Renal Disease equation version 4.

Endocrinology

Follicle-stimulating hormone (FSH) for post-menopausal women only¹

Post-menopausal is defined as amenorrheic for at least 1 year AND have a serum FSH level of > 20 mIU/mL.

Hematology

Hematocrit Hemoglobin

Platelets Red blood cell count

White blood cell count and differential

Urinalysis

Bilirubin Blood
Glucose Ketones
Leukocyte esterase Microscopy¹

Nitrite pH

Protein Specific gravity

Urobilinogen

Additional Urinalysis

Urine drug screen

Percent change in urine albumin-to-creatinine ratio (UACR) for spot urine specimen UACR for 24-hour urine specimen

Microscopy is performed only as needed based on positive dipstick test results.

Coagulation

Activated partial thromboplastin time

International normalized ratio

Prothrombin time

Serology

Hepatitis B surface antigen

Human immunodeficiency virus

Hepatitis C virus

Biomarkers

Aldosterone Renin

Serum/plasma samples taken during the study will be stored at a central laboratory for determination of various additional biomarkers, including but not limited to galectin-3, N-terminal of the prohormone brain natriuretic peptide, interleukin-6, collagen biomarkers, and C-reactive protein. The panel of biomarkers and time points for analysis will be determined prior to the database lock.

Pregnancy Test

Serum/urine pregnancy tests will be administered to all women patients of childbearing potential.

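### UACR is planned as both change and percent change with no lead scale and no log-ratio analysis, and the own-baseline covariate for secondary variables is not written (minor, secondary endpoints only)

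*Combined protocol and SAP*

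**What the plan says.** Section 7.2 lists, among the key secondary efficacy variables, "Change and percent change in UACR from baseline to Day 84 (for patients with albuminuria" or microalbuminuria). Together the two groups are patients with UACR of at least 30 mg/g. The synopsis and Section 2.2 carry the same pair of scales. None of these places ranks them.

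On analysis, Section 9.2.2.2 and the synopsis say: "For continuous secondary efficacy variables, the same ANCOVA model will be used as the primary efficacy analysis". The model carried over from Section 9.2.2.1 has treatment, eGFR level and background medication "as factors, and the baseline SBP value as a covariate". No log, ratio or geometric-mean analysis of UACR appears anywhere in the text.

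Section 9.2.1 sets baseline at Day 1, with the last pre-dose value as fallback, and plans summaries of "baseline efficacy variables (such as SBP, serum potassium, eGFR, creatinine, DBP, and UACR"). It does not say that each variable's own baseline enters its model.

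Two urine specimens are collected. The unqualified UACR sample is taken at Screening, Days 1, 7, 14, 28, 42, 56, 84 and 112, and Early Termination. The other is always labelled, as in "24-hour urine for UACR" (Section 6.4.10) and "24-hour urine samples for UACR" (Appendix A), and is taken only at Days 1, 42 and 84. Appendix B lists "Percent change in urine albumin-to-creatinine ratio (UACR) for spot urine specimen" and gives 24-hour UACR as a separate item.

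**The concern.** A change in mg/g and a percent change can answer differently on the same data. Raw change is dominated by patients with very high baseline UACR. Percent change is skewed to the right. If one interval excludes 0 and the other does not, the plan has no rule for which is the UACR result, and the choice would be made after the data are seen. Section 1 reports a UACR reduction in an earlier study of KBP-5074, so this result will be read closely.

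Read literally, Section 9.2.2.2 also adjusts UACR, DBP and the ABPM variables for baseline SBP and not for their own baseline, which is usually the stronger predictor of the Day 84 value.

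The stakes are confined to secondary variables: some loss of precision, and an avoidable choice between two versions of one result.

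**Working it through.** **The plan's own figure.** The documents give a sample size for SBP only. For 5 mmHg and SD 15, the 95% CI just excludes 0 at 2 × (1.96 × 15 / 5)² = 69.15, so 70 per group. With 15% added, 70 × 1.15 = 80.5, so 81, as in Table 2 (80 planned). The figure reproduces and does not depend on anything below.

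**Assumed inputs for UACR (none is in the documents).** 60 patients per arm; baseline log-normal, median 300 mg/g, log-SD 1.3, truncated at 30 mg/g; true reduction 30% in every patient (ratio 0.70); SD of log change 0.6 or 0.8; correlation of log change with log baseline −0.2; SBP independent of UACR. One dose against placebo, ANCOVA, two-sided 5%, 20,000 simulated trials per main cell.

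| Scale | Covariates | Power, SD 0.6 | Power, SD 0.8 |
|---|---|---|---|
| Raw change | SBP | 37.5% | 24.7% |
| Raw change | SBP + own baseline | 48.2% | 29.2% |
| Percent change | SBP | 84.0% | 54.9% |
| Percent change | SBP + own baseline | 84.1% | 55.2% |
| Log ratio | SBP | 89.7% | 67.6% |
| Log ratio | SBP + log baseline | 90.5% | 68.9% |

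Scale therefore matters far more than covariate. Adding own baseline helps raw change by 11 or 5 points and the other scales by about 1 point or less. For percent change to match the log ratio, the patient ratio is ((1.96 + z(power, log)) / (1.96 + z(power, percent)))² = 1.23 (SD 0.6) or 1.39 (SD 0.8).

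**Sensitivity.** I varied one input at a time: 40 to 70 per arm, median 150 to 600 mg/g, log-SD 1.0 to 1.6, correlation 0 to −0.4. The log ratio gains 32 to 65 points over raw change and 5 to 19 over percent change. A second simulation with a different data model (50 to 68 per arm, ratio 0.70 to 0.75) gave 15% to 40% for raw change, 35% to 88% for percent change and 47% to 93% for the log ratio.

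**Cases that do not favour the log scale by construction.**
- Percent change itself normal (SD 30 to 50%, shift 15 to 30 points): percent 77% to 93%, log 72% to 89% (3 to 6 points lower), raw 30% to 42%.
- Effect of 0 to 10% up to 300 mg/g and 40% above: raw 30% to 49%, percent 21% to 59%, log 43% to 81%.

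**Disagreement between the two planned scales (SD 0.6 / 0.8).**
- Uniform 30% effect: percent change alone excludes 0 in 48% / 35% of trials, raw change alone in 1.8% / 4.4%. The sum is about 50% / 39%.
- No effect up to 300 mg/g and 40% above: raw alone 21% / 19%, percent alone 13% / 9%.

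Which scale misses the effect depends on the form of the effect.

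**No true effect.** Each model alone rejects in 3.6% to 5.2% of trials. At least one of raw and percent change excludes 0 in 7.4% / 7.9%. If the two were independent the figure would be 1 − 0.95² = 9.75%; they are correlated, so it is lower.

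**The case against.** Five points can be made on the other side.

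- **This is Phase 2, and multiplicity adjustment is expressly waived.** That stands as an answer to any demand for alpha control, and none is made here. The 8% counts both directions; a false benefit on at least one scale occurs in about 3.7% / 3.6% of null trials, against a nominal 2.5%. But waiving adjustment does not say which scale gives the UACR result.
- **Preferring the log scale is a choice.** This stands in part. Every UACR input is assumed, and naming percent change alone as lead would also remove the ambiguity. The log ratio was best, or within 6 points of best, in every case run, which supports a recommendation but does not show an error in the plan.
- **Own baseline was surely intended.** Probably so, given Section 9.2.1. A reader might infer a real loss of power for DBP and ABPM. That loss exists only on the literal SBP-only reading and vanishes on the natural one.
- **Spot urine is already the evident specimen.** This largely stands: the protocol uses the bare term for the routine sample, labels the 24-hour one each time, and ties percent change to spot urine in Appendix B. A reader might infer two scales times two specimens, hence four competing results per dose and a still higher error rate. No section says that 24-hour UACR is tested as an equal version. What remains is that the efficacy sections name no specimen.
- **Naming a lead is not enough to define the analysis.** Correct: the visit that defines the UACR subset and the handling of a missing Day 84 UACR also need a sentence each.

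**Conclusion.** The point holds as a minor improvement to a key secondary endpoint. UACR has two unranked scales, no log-ratio analysis, and an own-baseline covariate that is natural but unwritten. On the assumed inputs with a uniform 30% reduction, a log ratio adjusted for log baseline and SBP has about 90% / 69% power, against 84% / 55% for percent change and 37% / 25% for raw change under the SBP-only model. With no effect, one or other planned scale excludes 0 in about 8% of trials. The sizes depend on the assumptions; the missing lead is a matter of text.

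A reader might go further and conclude that raw change is always the scale that fails. That is true under a uniform proportional effect, but when the effect is confined to high UACR, percent change can be the one that misses it. Nor does the point reach the primary SBP analysis, whose model states its own covariate, or the sample size in Section 9.2.7.

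**What to change.** In Section 9.2.2.2 and the synopsis, state that:

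1. Each continuous secondary efficacy variable uses the primary ANCOVA with its own baseline added and baseline SBP kept. SBP stays because Section 3.1 says "Randomization will be stratified to balance enrollment for key variables that may influence safety and/or efficacy evaluations", SBP is one of the two factors (also Section 5.3), and baseline SBP is the only model term that reflects it.
2. The lead UACR analysis is log(Day 84 / baseline) from the spot specimen, adjusted for log baseline UACR and baseline SBP. It is reported as a geometric mean ratio to placebo with 95% CI, back-transformed to percent change.
3. The UACR subset (at least 30 mg/g) is defined by the Day 1 spot baseline under Section 9.2.1, and a missing Day 84 UACR follows the same rule as the primary endpoint.
4. Raw change, arithmetic percent change and 24-hour UACR are supportive.

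Spot urine suits the lead because it alone is collected at Screening (a fallback baseline), at every scheduled clinic visit on treatment other than the ABPM-only visits, and at Early Termination. Align the UACR wording in the synopsis, Sections 2.2 and 7.2, and Appendix B.

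The cost is a few sentences and no new data. The UACR result becomes a ratio rather than mg/g, one degree of freedom goes to the added covariate, and 3 to 6 points of power are lost if percent change is itself symmetric. If the sponsor prefers percent change, naming it alone as lead also removes the ambiguity.
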